### *Sample Size Calculation*

Because participants will serve as their own control, individual variability in experiencing and reporting pain will be reduced, enhancing our ability to identify treatment effects. A sample size of 32 patients will give us 80% power to observe a 30% difference in delta pain scores (our primary outcome). As many patients will be discharged prior to being able to complete the study. We will aim for an enrollment of 60 total patients.

### *Research Related Risks*

1. Loss of Confidentiality: There is a minimal risk for a loss of confidentiality when participating in a research study. However, every step to ensure the confidentiality and anonymity of results and identity will be taken. Steps will include using only an assigned code number for personally identifiable information, including contact information and name, on any documentation from this study. Moreover, electronic data will be password-protected and all paper copies of data will be stored in a locked cabinet.

2. There is a minimal risk for a breach of privacy. However, to minimize this, consent will only be obtained in private patient rooms or in a private conference room.

3. There is a risk that patients may have a difficult time using the HMD and handheld controller, which may make them frustrated or upset. At this point, the research personnel will assist them in any way they can so that the patient can use the HMD and continue on with the study protocol. The research personnel is aware that the device can be difficult to use for first time users. The PI and research personnel have developed standards of procedures on how to address this issue if it were to arise.

4. Immersion in virtual reality may cause of a sense of being in a closed environment and rarely nausea. These effects are only transitory but if you experience any discomfort, the virtual

reality headset can be removed quickly. Patients who cannot tolerate the virtual reality will prematurely end study participation.

5. Although uncommon, patients could potentially experience seizure like activity while using the HMD. Of note, the HMDs are widely available and used by the public in everyday life and require no special screening or monitoring for seizure in their use. Per the Oculus Rift product description, "Some people (about 1 in 4000) may have severe dizziness, seizures, eye or muscle twitching or blackouts triggered by light flashes or patterns, and this may occur while they are watching TV, playing video games or experiencing virtual reality, even if they have never had a seizure or blackout before or have no history of seizures or epilepsy". The PI and research personnel will ensure that patients do not suffer from seizures prior to their enrollment. During the study protocol procedures, the patient will be monitored in a hospital bed where there is extensive experience in monitoring for and treating seizures. Seizures from virtual reality headset use are known to occur in patients with photosensitive epilepsies. Traumatic brain injury is not known to produce photosensitive epilepsy. If at any time, the patient develops severe dizziness, seizures, eye or muscle twitching or blackouts triggered by light flashes or patterns the virtual reality headset will be removed and the study will be discontinued in the patient.

*Primary and Secondary Analyses*

Descriptive statistics will be used to describe the patient population. The primary outcome (Aim 1a) is the difference in change in pre- and post-session pain scores in the immersive virtual reality sessions as compared to control sessions. Secondary outcomes will include opioid usage (Aim 1b), affective measures (mood and anxiety), autonomic measures, and subjective experience measures (Aim 1c). We will use mixed effect models to analyze the differences between the ratings over time. This model allows us to run analyses utilizing all subjects despite some missing measurements (which can be expected when studying patients in an ICU setting). To investigate if demographics or patient measures of gaming addiction, suggestibility, or expectancy are related to the pain effect, we will use Pearson's correlation between the questionnaire scores and the difference of the means of both conditions and virtual reality sessions.

#### *Data collection*

All source data and research documentation will be kept in a locked cabinet in the research coordinator's locked office which is in a locked office suite. Electronic data will be kept on a desktop computer which is encrypted and password-protected by the guidelines implemented from the University of Maryland School of Medicine. To ensure confidentiality, all data files will only be accessible to the research team.

#### *Data monitoring*

This study will be reviewed weekly by the primary investigator to assess for adverse events. An interim analysis will be conducted when 20 patients with non-TBI injuries and 20 patients with TBI have been enrolled. Safety monitoring results will be reported to the IRB.

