### *Eligibility Criteria*

#### Inclusion Criteria

Diagnosis of Traumatic Injury (including but not limited to traumatic brain injury)

Age greater than or equal to 18 years-old

Endorsing at least moderate pain as defined by documentation of at least one numeric rating pain scale score of 3 or more in the last 24 hours.

Glasgow Coma Scale of 15

Expected to stay in the hospital for at least twelve hours after enrollment

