### *Procedures*

Patients who are enrolled in the study will be identified as candidates via the PI or Sub-Investigator, or Research Coordinator. Once the patient has been identified, the research coordinator, PI, or Sub-Investigator will approach the patient and discuss the research protocol with them. If the patient agrees to participate, the study coordinator will make sure that all of the appropriate documentation (including consent) is completed before study procedures begin.

After the consent has been signed and completed, the study participant will complete a pre-study questionnaire to elicit their prior experience with the proposed therapeutic as well as several validated scales of pain, nausea, anxiety and depression, gaming addiction, suggestibility, and expectancy. They will then be given a tutorial on how to use the Virtual Reality Headset, or Head Mounted Display (HMD). The HMD that will be used for this study protocol is not limited to just the Oculus Rift or Rift S, but may also be the Samsung Odyssey Plus, and HTC Vive Pro. The research staff will go over specifics on how to use the HMD, and will remain throughout the duration of time the participant is in the virtual reality world in case they have any questions or concerns.

Once the participant is acquainted with the HMD, by completing their guided tutorial on how to use the headset, he or she will take part in two virtual reality sessions and two non-immersive tablet-based control sessions. One session will be meditative, where the second session will be chosen during the participants tutorial/introduction to the HMD. This environment could be a game, music, or relaxing. There will be two sessions per day including one virtual reality session and one non-immersive tablet based sessions. The virtual reality sessions and non-immersive tablet-based sessions will take place within the duration of their hospitalization. Sessions will be randomized using internet-based randomization techniques, or through mathematical programs. Participants will be allowed to complete more sessions if they desire once they complete their initial 2 VR sessions and 2 tablet-based sessions.

[figure not shown]
To be completely immersed during the sessions, the patient will also be given the option to use Noise Cancelling Headphones during the study. Some HMD headsets come with headphones attached, and some do not. The Noise Cancelling Headphones will be used with the HMD's

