#### *Device safety*

The Oculus Rift is a commercially available portable VR headset device for gaming and relaxation with nonsignificant risks. There is a precedent of using VR in hospitalised medical patients. In a 2018 review of 11 randomised controlled trials (including nearly 500 patients) that used VR in hospitalised patients found the VR to be feasible in the hospital and safe. A 2010 study evaluating VR for acute pain management after trauma did not include patients with TBI and found no safety concerns. Similarly, a review of 11 studies of VR for TBI rehabilitation found no safety concerns. We therefore believe VR to be safe in the acute phase after TBI.

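### Does the interim look need a quota or a fallback, given that it waits for 20 TBI and 20 non-TBI patients within a planned 60?

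*Combined protocol and SAP*

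**What the plan says.** The whole interim provision is one sentence in the Data monitoring section: "An interim analysis will be conducted when 20 patients with non-TBI injuries and 20 patients with TBI have been enrolled". Both counts must reach 20, so at least 40 patients must be enrolled. The section states neither what the look is for nor what decision could follow from it. The sentence before it sets up a separate safety process, "This study will be reviewed weekly by the primary investigator to assess for adverse events", and the sentence after it sends safety monitoring results to the IRB.

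The Sample Size Calculation section gives the total, "We will aim for an enrollment of 60 total patients", with no division by injury type. The Inclusion Criteria admit any trauma patient: "Diagnosis of Traumatic Injury (including but not limited to traumatic brain injury"), with no quota or cap. Under Procedures, recruitment is in the hands of study staff, "Patients who are enrolled in the study will be identified as candidates via the PI or Sub-Investigator, or Research Coordinator", with no rule about TBI status. The same section randomizes sessions within a patient: "Sessions will be randomized using internet-based randomization techniques, or through mathematical programs".

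**The concern.** A trigger that needs a minimum in each of two groups is reached only if the mix of patients allows it. Here the mix is left open, and no alternative trigger applies if one group is scarce. With an uneven mix, the look could come so late that few patients remain, or not come at all.

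What would be lost is the only review in the plan that is linked to TBI status. That could matter because the safety evidence for acute TBI is indirect. The Device safety section says of the nearest comparable work: "A 2010 study evaluating VR for acute pain management after trauma did not include patients with TBI and found no safety concerns". The natural suggestion is to add a fallback, for example a look at 50 enrolled if 20 and 20 has not been reached by then.

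**Working it through.** **Inputs.** Trigger: at least 20 in each group (Data monitoring). Planned total: 60 (Sample Size Calculation). TBI share: not in the documents, so it is assumed and varied. The plan gives no probability or timing for the look, so there is no stated figure to reproduce.

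**When the look is missed.** Let X be the TBI count at 60. The look needs X ≥ 20 and 60 − X ≥ 20, that is 20 ≤ X ≤ 40. It is missed if X ≤ 19 or X ≥ 41. The earliest possible time is patient 20 + 20 = 40, which is 40/60 = 67% of planned enrolment.

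**How likely that is.** Suppose patients enter independently with a fixed share p in the rarer group and staff do not steer the mix. Then X is Binomial(60, p) and P(reached by 60) = P(20 ≤ X ≤ 40). If T is the enrolment number at which both counts first reach 20, the mean number still to come is E[60 − T | T ≤ 60].

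| Share of rarer group (assumed) | Reached by 60 | Missed | Mean still to enrol, if reached | Median enrolment at trigger |
|---|---|---|---|---|
| 50% | 99.4% | 0.6% | 15 | 44 |
| 40% | 88.3% | 11.7% | 11 | 49 |
| one third | 54.8% | 45.2% | 8 | 59 |
| 30% | 33.1% | 66.9% | 6 | 66 |
| 25% | 9.2% | 90.8% | 5 | 79 |

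A 90% chance of reaching 20 and 20 by 60 needs a TBI share between about 41% and 59%. The answer therefore runs from negligible to near certain, depending on a number the documents do not contain.

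**What a fallback at 50 would do.** It sets the timing whenever 20 and 20 has not been reached by patient 50. Those cases are of two kinds: the look would still have come between 51 and 60 (it is pre-empted), or it would never have come by 60 (it is rescued).

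| Share | Fallback sets the timing | Pre-empts a look at 51 to 60 | Rescues a missed look |
|---|---|---|---|
| 50% | 11.9% | 11.3% | 0.6% |
| 40% | 44.8% | 33.1% | 11.7% |
| one third | 80.4% | 35.2% | 45.2% |
| 25% | 98.6% | 7.9% | 90.8% |

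At 50% and 40% it replaces a full 20-and-20 look more often than it rescues one. At one third and below the order reverses.

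**What it costs in group size.** At a one-third share, the mean size of the rarer group at fallback looks is 15.5. For a fallback at 45 or 55 it is 14.5 or 16.2. If the look is read as a safety look, the one-sided 95% upper limit with zero events is 1 − 0.05^(1/n): 13.9% at n = 20, 17.1% at n = 16 and 22.1% at n = 12.

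**A cap instead.** Limiting each group to 40 guarantees 60 − 40 = 20 in the other group by patient 60. But the condition may be met only at patient 60, when nothing is left to monitor, and a cap turns away eligible patients.

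**The case for a change.** The strongest case for a change is that the gap is real and cheap to close. The thresholds of 20 and 40 are exact, and the plan contains no quota, cap or fallback. The 20-and-20 rule shows that the sponsor wanted both groups represented at the look. The Background section says that VR has not been studied for headache pain caused by TBI. At a one-third share, the look would be missed almost half the time. One added clause would leave sample size and final analysis untouched.

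The arithmetic stands, and so does the point that the mix is not guaranteed. What does not follow is that a miss is likely or that it would do harm. Every percentage assumes that staff recruit without regard to a milestone written into their own protocol. The Device safety section also cites a review of 11 studies of VR in TBI rehabilitation that found no safety concerns. Rehabilitation is not the acute phase, but the evidence in TBI is not empty. Nor is a fallback a guarantee, since it fails if enrolment stops before 50 without 20 in each group. The more basic gap, that the look has no stated purpose, would remain after either remedy.

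**Conclusion.** No change is needed. With 60 enrolled, the look is missed if the TBI count is below 20 or above 40. For assumed rarer-group shares from 50% down to 25%, that has a chance between 0.6% and 91%, given independent enrolment at a fixed share and no steering by staff. The documents support no particular point in that range.

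The consequence is limited wherever the truth lies. No decision hangs on the look. Adverse-event review and IRB reporting do not depend on it. The primary outcome compares sessions within the same patient, so the injury mix does not decide whether that comparison is valid, provided the look is not used to test efficacy. Following the plan as written makes no result of the trial wrong.

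Staff can fill the gap sensibly by watching the two counts and recruiting towards 20 in each, or by letting enrolment run a little past the aim of 60. A fallback trades group size for earlier timing, and a cap trades timing for group size. Choosing between them, or leaving the rule alone, is a matter of judgement for the sponsor.

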#### *Device safety*

The Oculus Rift is a commercially available portable VR headset device for gaming and relaxation with nonsignificant risks. There is a precedent of using VR in hospitalised medical patients. In a 2018 review of 11 randomised controlled trials (including nearly 500 patients) that used VR in hospitalised patients found the VR to be feasible in the hospital and safe. A 2010 study evaluating VR for acute pain management after trauma did not include patients with TBI and found no safety concerns. Similarly, a review of 11 studies of VR for TBI rehabilitation found no safety concerns. We therefore believe VR to be safe in the acute phase after TBI.
